11.1.1 Adverse Events (AEs)

AE means any untoward medical occurrence associated with the use of an intervention in humans, whether or not considered intervention-related in a patient or clinical investigation subject administered a pharmaceutical product regardless of its causal relationship to the study treatment.

An AE can therefore be any unfavorable and unintended sign (including an abnormal laboratory finding), symptom or disease temporarily associated with the use of a medicinal (investigational) product. The occurrence of an AE may come to the attention of study personnel during study visits and interviews of a study recipient presenting for medical care, or upon review by a study monitor. AEs, including solicited local and systemic (subjective and quantitative) reactions, not meeting the protocol-defined criteria for SAEs will be recorded on the appropriate DCF and entered into the electronic case report form (eCRF). Information to be collected for unsolicited non-serious AEs includes event description, date of onset, licensed study physician's assessment of severity and relationship to GRT-R910 or alternate etiology (if not related to study product) (assessed only by those with the training and authority to make a diagnosis), date of resolution, seriousness, and outcome. AEs occurring during the trial collection and reporting period will be documented appropriately regardless of relationship to GRT-R910. AEs will be followed through resolution.

Any medical condition that is present at the time that the subject is screened will be considered as baseline and not reported as an AE. However, if the severity of any pre-existing medical condition increases, it should be recorded as an AE.

If an event meets both the criteria of a study endpoint and an adverse event, the event will be reported either as a study endpoint or as an AE (not both).

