12.4.2 Analysis of the Primary Endpoint(s)

Summaries and analysis of safety data will be presented for the Safety Analysis Population.

Solicited reactogenicity signs and symptoms (local and systemic) will be summarized by severity for each day post GRT-R910 vaccination (Days 1-8) and as the maximum severity over all 7 days. Additionally, solicited AEs will be analyzed by taking the most severe response over the follow-up period, dichotomizing into a binary variable (none versus mild, moderate, or severe) and using standard techniques, such as exact confidence intervals (CI), to summarize the proportion of subjects reporting each symptom, any application site symptom, and any systemic symptom.

Unsolicited non-serious AEs will be collected from the time of GRT-R910 vaccination through 28 days after GRT-R910 vaccination. Unsolicited AEs will be coded by MedDRA for preferred term and system organ class (SOC). All SAEs will be collected from the time of GRT-R910 vaccination through the end of the study. SAEs will be described by detailed listings showing the event description, MedDRA preferred term and SOC, relevant dates (vaccinations and AEs), severity, relatedness, and outcome for each event. Non-serious unsolicited AEs will be summarized as number and percentage of subjects reporting at least 1 event in each MedDRA preferred term and SOC, cross tabulated by severity and relationship to study product. Additionally, the proportion of subjects and exact 95% CIs of AEs in aggregate and by MedDRA categories will be computed.

Clinical laboratory data will be summarized as change from baseline and by severity for each visit, and as the maximum over all post-vaccination visits.

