The purpose of this statistical analysis plan (SAP) is to define the planned statistical analysis of the study data consistent with the safety study objectives. Therefore, analysis for immunogenicity will be described in a separate SAP.

References throughout this SAP to specific visits by study day (e.g., Day 1) refer to study day as defined in schedule of events in [Appendix 1](#).

2. Objectives and Endpoints

Objectives	Endpoints (Outcome Measures)
Primary	

 • To assess the safety and tolerability of 2 different doses (10 or 30 mcg) of GRTR910 when administered to healthy adults ≥ 60 years of age who were previously vaccinated with a first-generation COVID-19 vaccine (Cohorts 1 and 2; AstraZeneca) • To assess the safety and tolerability of a 10 mcg dose of GRT-R910 when administered to healthy adults (≥ 18 years of age) who were previously vaccinated with either an adenoviral COVID-19 vaccine (AstraZeneca, Janssen) or an mRNA-based COVID-19 vaccine (Pfizer/BioNTech, Moderna) 	
 • Occurrence of solicited local reactogenicity signs and symptoms for 7 days after GRT-R910 vaccination • Occurrence of solicited systemic reactogenicity signs and symptoms for 7 days after GRT-R910 vaccination • Occurrence of unsolicited AEs for 28 days after last study-administered GRT-R910 vaccination • Change from baseline for clinical safety laboratory parameters 7 days after last study-administered GRT-R910m vaccination • Occurrence of SAEs and adverse events of special interest (AESIs), including potentially immune-mediated medical conditions (PIMMCs), medically attended adverse events (MAAEs), and new onset chronic medical conditions (NOCMCs), throughout the entire study after GRTR910 vaccination
Secondary	

 • To assess the cellular and humoral immunogenicity of GRT-R910 when administered to volunteers (≥ 60 years of age for Cohorts 1, 2, 3, and 4 and ≥ 18 to ≤ 59 years of age for Cohort 6) who were previously vaccinated with either an adenoviral COVID-19 vaccine (AstraZeneca, Janssen) or an mRNA-based COVID-19 vaccine (Pfizer/BioNTech, Moderna) 	
 • Response rate, and magnitude of SARS-CoV-2-specific antibody binding and neutralization in serum samples. • Response rate, magnitude, and breadth of SARS-CoV-2 specific T-cells as assessed by interferon (IFN)-enzyme-linked immunospot (ELISpot) for 10 subjects per cohort
[REDACTED]	

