9.1.2. Solicited Adverse Events

Solicited AEs are anticipated local and systemic AEs for which consistent collection of information is desired. Study clinicians will follow and collect resolution information for any reactogenicity symptoms that are not resolved within 7 days post GRT-R910 vaccination (day of vaccination and 7 subsequent days).

Solicited AEs (i.e., reactogenicity) will be collected using a memory aid and recorded on the appropriate DCF from the time of GRT-R910 vaccination within 7 days after each GRT-R910 vaccination.

For this study, solicited AEs will be:

- Injection site pain
- Injection site tenderness
- Injection site erythema
- Injection site edema/induration
- Headache
- Fatigue
- Malaise
- Myalgia
- Arthralgia
- Nausea
- Chills
- Fever

The toxicity grade for fever will be derived from temperature per FDA guidance [7]:

Vital Signs	Mild (Grade 1)	Moderate (Grade 2)	Severe (Grade 3)	Potentially Life Threatening (Grade 4)
Fever (°C)	38.0 – 38.4	38.5 – 38.9	39.0 – 40	> 40
(°F)	100.4 – 101.1	101.2 – 102.0	102.1 – 104	> 104

Temperatures will be recorded by oral thermometer and only the highest temperature will be recorded.

Reactogenicity local reactions including erythema, induration/edema, pain, and tenderness.

Reactogenicity systemic reactions including fever, chills, fatigue, malaise, myalgia, arthralgia, headache, and nausea.

Reactogenicity reactions that cannot be classified in any of the aforementioned categories for local and systemic events will be reported and summarized as unsolicited adverse events, and presented in a separate listing.

Any serious reactogenicity will be reported and summarized as serious unsolicited adverse event (SAE) (section [9.1.1.3](#)).

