The number and percentage (with 95% Clopper-Pearson CIs [6]) of participants who reported any solicited AE on the vaccination day and through the 7 subsequent days (see the exact windows for each cohort in [Table 5](#)) will be tabulated by grade and treatment group for each vaccination. Percentages will be based upon the number of participants in the Safety Analysis Set within each vaccination group. Subjects will be counted once for the most severe event in cases where the subject reported more than one event per solicited AE category (e.g., injection site pain). In addition, the duration (in days) of solicited AEs after each vaccination will be summarized by treatment group for each vaccination. Duration will be calculated as the number of days of the Solicited AE during the special window ([Table 5](#)).

Table 5 Windows for solicited AEs per Cohort

Cohort	Vaccination Day	Windows for Solicited AEs
1 and 2 (Subjects NOT RECEIVING booster dose)	Day 1	Day 1 through Day 8
1 and 2 (Subjects RECEIVING booster dose)	Day 1	Day 1 through Day 8
	Day 113	Day 113 through Day 120
3, 4, and 6	Day 1	Day 1 through Day 8
	Day 29	Day 29 through Day 36

All solicited local and systemic AEs will be presented in the data listings, including a listing of solicited AEs.

Calculation of Solicited AEs duration

The number of days will be calculated at the level of subject, vaccination (prime or booster), and symptom as the longest duration of consecutive days after the injection (including the day of injection) the subjects' reported solicited AE occurs with a toxicity grade > 0. If the solicited AE continues beyond 8 days, the days from the solicited AE reported after 8 days will be included (e.g., an event that lasted 5 days in the first 8 days post injection and 4 days beyond 8 days post injection, the duration will be reported as >8 days). A separate example below illustrates how solicited AE duration is calculated:

Subject ID	Prime/Booster	Symptom	Timepoint	Severity	Grade
G0910000999	DOSE 1	Headache	Day 1	MILD	1
G0910000999	DOSE 1	Headache	Day 2	MILD	1
G0910000999	DOSE 1	Headache	Day 3	NONE	0
G0910000999	DOSE 1	Headache	Day 4	NONE	0
G0910000999	DOSE 1	Headache	Day 5	MILD	1

G0910000999	DOSE 1	Headache	Day 6	MODERATE	2
G0910000999	DOSE 1	Headache	Day 7	MODERATE	2
G0910000999	DOSE 1	Headache	Day 8	MILD	1
G0910000999	DOSE 1	Headache	Day 9	MILD	1
G0910000999	DOSE 1	Headache	Day 10	NONE	0

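### SAP 9.1.2 files serious solicited reactions as unsolicited SAEs and does not say whether they stay in the solicited tables

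*SAP*

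**What the plan says.** Solicited reactogenicity is a primary endpoint. The systemic half reads "Occurrence of solicited systemic reactogenicity signs and symptoms for 7 days after GRT-R910 vaccination" (SAP section 2), and the local half is parallel. SAE occurrence is a separate primary endpoint in the same table.

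Two documents set the analysis of the solicited endpoint:

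- Protocol 12.4.2: "solicited AEs will be analyzed by taking the most severe response over the follow-up period", then dichotomised and summarised with exact intervals.
- SAP 9.1.2, tabulation paragraph: "Subjects will be counted once for the most severe event in cases where the subject reported more than one event per solicited AE category". The denominator is fixed: "Percentages will be based upon the number of participants in the Safety Analysis Set within each vaccination group".

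Neither mentions seriousness. Earlier in SAP 9.1.2, however, stands the routing sentence: "Any serious reactogenicity will be reported and summarized as serious unsolicited adverse event (SAE"), with a pointer to the SAE section. The sentence just before it sends reactions that fit none of the listed solicited categories to the unsolicited summaries, using the same verb phrase.

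Two sentences in Protocol 11.1.1 bear on the reading. One gives the ordinary recording route for AEs, solicited ones included, "not meeting the protocol-defined criteria for SAEs will be recorded on the appropriate DCF". The other covers an event that is both a study endpoint and an AE: "the event will be reported either as a study endpoint or as an AE (not both").

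**The concern.** The routing sentence does one thing explicitly and leaves another open. Explicitly, it labels a reaction to a solicited term as unsolicited because it was serious. The event then counts in summaries meant for unsolicited events. What it leaves open is whether the event is also kept in the solicited tables.

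The reading that drops it is a natural one. In the preceding sentence the same verb phrase plainly means instead of the solicited tables, and nothing signals a change to in addition to them. The protocol's separate recording route for non-serious reactions points the same way.

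If the event is dropped, the solicited tables can only move down, because the subject stays in the denominator and shows no event, or a lower grade if another record exists in that category. The longest-episode duration could also shorten. Reactogenicity after the first dose is one of the inputs that Protocol 6.1 names for choosing the dose in future studies, so the solicited tables should be complete in themselves.

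**Working it through.** **1. The plan's own figure.** Protocol 12.2 and SAP 4.3 give an 89% chance of at least one event in 10 subjects at a true rate of 20%. Check: 1 − (1 − 0.20)^10 = 89.26%. It reproduces, as do all 21 cells of the accompanying table. It fixes the scale: with 10 per cohort, one subject is 10 percentage points.

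**2. The texts side by side, for a solicited term that meets SAE criteria inside the SAP Table 5 window.**

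| Text | What it implies |
|---|---|
| Protocol 12.4.2 | Counted in the solicited analysis at maximum severity |
| SAP 9.1.2, tabulation paragraph | Counted once, at its most severe grade |
| SAP 9.1.2, routing sentence | Summarised as a serious unsolicited event; silent on the solicited tables |
| Protocol 11.1.1, recording route | Non-serious solicited reactions go on the ordinary form; Protocol 11.1.2 has a separate SAE form |
| Protocol 11.1.1, either/or sentence | One or the other, without saying which when both categories are endpoints |
| Protocol 11.1.1.1 | Memory-aid collection; no reclassification of serious events |
| SAP section 11 | Lists three changes to the planned analysis; this is not among them |

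The first two rows and the third cannot all be followed if the third means instead of.

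**3. Size of one moved event.** Inputs: n = 10 per cohort (Protocol Table 4), Clopper-Pearson 95% intervals (SAP Table 2) and a fixed Safety Analysis Set denominator. Assumption: one subject has a serious reaction and no other record in that row.

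- Kept, 1/10 = 10.0%. Lower limit 1 − 0.975^(1/10) = 0.25%. The upper limit solves (1 − p)^10 + 10p(1 − p)^9 = 0.025, giving 44.50%.
- Moved, 0/10 = 0%. Upper limit 1 − 0.025^(1/10) = 30.85%.

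With two events of which one is moved, 2/10 = 20.0% (2.52 to 55.61) becomes 1/10 = 10.0% (0.25 to 44.50).

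If the 10 mcg prime is pooled over Cohorts 1, 3, 4 and 6, assuming 40 subjects, 1/40 = 2.5% (0.06 to 13.16) becomes 0/40 = 0% (0 to 8.81).

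**4. Where the event would still be seen.** SAP Appendix 2 plans serious TEAE tables, overall and treatment-related (14.3.1.12 and 14.3.1.13), and matching listings (16.2.7.5 and 16.2.7.6). No planned output title identifies an SAE as a solicited reaction. If the event is also Grade 3, it falls under the unsolicited severe summaries (14.3.1.14.1 and 14.3.1.14.2).

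**The case against.** The strongest reply is that the SAP never orders removal. The routing sentence does not say that the event is excluded from the solicited tables. The tabulation paragraph covers participants with any solicited AE, makes no exception, and is followed by a promise to list all solicited events. The worked duration example has symptom, day, severity and grade columns but no seriousness field, and the fever scale runs to Grade 4. A serious fever written in the memory aid therefore qualifies as the text stands. The Protocol 11.1.1 recording sentence concerns forms, not analysis. The either/or sentence does not settle the matter, since solicited reactions and SAEs are both primary endpoints. The preceding sentence about unclassifiable reactions moves nothing that was ever solicited.

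Most of this stands. Removal is a plausible reading, not an instruction. But the reply does not answer the relabelling, which is explicit, and it does not tell the programmer which sentence governs.

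A reader might also infer two stronger things:

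- **That the worst reactions disappear.** Seriousness and severity are separate determinations (Protocol 11.1.4). A non-serious Grade 3 or 4 reaction stays in the solicited tables, and a serious one may be of lower grade. Protocol 4.3.3 reports an SAE of Grade 2 fever, though after a different product given with nivolumab.
- **That the rule favours the product on its primary safety reading.** SAE occurrence is itself primary, the event remains in the SAE outputs, and a related SAE within 28 days meets a halting criterion (Protocol 11.6.1). The study is descriptive and tests no hypothesis (Protocol 12.1).

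The documents support neither inference.

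**Conclusion.** The point holds as a classification defect with limited consequences. SAP 9.1.2 places serious solicited reactions among unsolicited events, has no basis for this in the protocol, and does not record it as a change. It also leaves unclear whether they remain in the solicited tables, against two passages that count the most severe event without exception.

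The consequence is possible under-counting in the solicited incidence, grade and duration summaries and over-counting in the unsolicited summaries. No event is lost from the report.

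The size is 10 percentage points per moved event in a cohort of 10. That figure assumes the dropping reading is programmed and that the subject has no other record in that row. To affect a severe-or-worse row, the event must be both serious and Grade 3 or higher. The documents give no expected frequency of serious solicited reactions. At n = 10 the intervals for 0 and 1 event overlap heavily, so this is a matter of correct counting, not of changing an inference.

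**What to change.** Replace the routing sentence in SAP 9.1.2 with:

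*A solicited reaction within the Table 5 window that meets SAE criteria is counted in all solicited tables at its maximum grade, is also shown in the SAE summaries flagged as solicited, and is not added to the unsolicited totals.*

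Reconcile this with the either/or sentence in Protocol 11.1.1, for example by stating in the SAP that it does not restrict showing one event under two safety endpoints.

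The cost is brief text edits, a solicited flag in the SAE programming, and a footnote explaining that such an event appears in two sets of tables. No new data are needed, provided that a reaction recorded as an SAE can be linked to its solicited term, vaccination and grade. That should be confirmed when the flag is programmed.

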Pre-administration reactogenicity assessments will be performed prior to each study vaccination to establish baseline, then the study vaccination will be given.

Subjects will be observed in the clinic for at least 45 minutes after GRT-R910 vaccination. The vaccination site will be examined, post-administration reactogenicity assessments will be performed, and any AE/SAEs will be assessed and recorded on the appropriate data collection form prior to discharge from the clinic. AESIs, including serologically or virologically confirmed SARS-CoV-2 infection and severity of COVID-19, PIMMCs, MAAEs, and NOCMCs will be collected from the time of first vaccination throughout the entire study. Any SAE occurring after signing of the ICF will be recorded and reported to the sponsor or designee by the investigator

within 24 hours of becoming aware of the SAE. If the SAE occurs after signing of the ICF and before the first (prime) dose, it will be reported on the medical history electronic case report form (eCRF). If the SAE occurs after the first (prime) dose, it will be reported on the AE eCRF.

All subjects will complete a subject memory aid through 7 days after each GRT-R910 vaccination. Subject memory aids will be reviewed with the subjects for AEs (solicited local and systemic reactions and unsolicited AEs) during telephone, e-mail, or text contacts or at a clinic visit, as appropriate.

Reactogenicity assessments will include an assessment of solicited AEs occurring from the time of GRT-R910 vaccination on Day 1 through Day 8 after GRT-R910 vaccination, which includes an assessment of local reactions including erythema (redness), induration (hardness)/edema (swelling), pain, and tenderness as well as systemic reactions including fever, chills (feverishness), fatigue (tiredness), malaise (general unwell feeling), myalgia (body aches/muscular pain exclusive of the injection site), arthralgia (joint pain exclusive of the injection site), headache, and nausea.

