9.1. Adverse Events

Adverse Event (AE) means any untoward medical occurrence associated with the use of an intervention in humans, whether or not considered intervention-related in a patient or clinical investigation subject administered a pharmaceutical product regardless of its causal relationship to the study treatment.

An AE can therefore be any unfavorable and unintended sign (including an abnormal laboratory finding), symptom or disease temporarily associated with the use of a medicinal (investigational) product. The occurrence of an AE may come to the attention of study personnel during study visits and interviews of a study recipient presenting for medical care, or upon review by a study monitor. AEs, including solicited local and systemic (subjective and quantitative) reactions, not meeting the protocol-defined criteria for SAEs will be recorded on the appropriate DCF and entered into the

eCRF. Information to be collected for unsolicited non-serious AEs includes event description, date of onset, licensed study physician's assessment of severity and relationship to GRT-R910 or alternate etiology (if not related to study product) (assessed only by those with the training and authority to make a diagnosis (date of resolution, seriousness, and outcome. AEs occurring during the trial collection and reporting period will be documented appropriately regardless of relationship to GRT-R910. AEs will be followed through resolution.

Any medical condition that is present at the time that the subject is screened will be considered as baseline and not reported as an AE. However, if the severity of any pre-existing medical condition increases, it should be recorded as an AE.

A treatment-emergent AE (TEAE) is defined as any new AE that begins after the first vaccination or any pre-existing condition that worsens in severity. A treatment related adverse event (TRAЕ) is defined as any AE that is deemed to be related to the vaccination.

Adverse events consist of solicited AEs (local and systemic), unsolicited treatment-emergent AEs, treatment-related AEs, severe AEs, SAEs, MAAEs, AESIs, AEs leading to withdrawal from study participation.

All AEs will be coded using the MedDRA (version to be delineated in the CSR), including System Organ Class (SOC) and Preferred Term (PT) names. Summary by SOC and PT will be shown in some tables. The data will also include AEs based on laboratory assessment (if applicable). All AEs will be followed through resolution.

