Only TEAEs will be included in summary tables and will be summarized by cohort and vaccination (Vaccination Dose 1, Vaccination Dose 2, entire study period). Percentages will be based upon the number of participants in the Safety Analysis Set within each cohort. A subject may have more than 1 AE for an SOC or PT. A subject with 2 or more AEs within the same level of summarization will be counted only once in that level 1

The rules described in [Table 4](#) will be applied for AEs partial dates during this study to understand if it is TEAE. No other data will be imputed.

All AEs will be reported by data listings for the SAF.

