In the above example, the duration of the headache for the subject at dose 1 (prime dose) is 5 days. Note that there are two solicited AE episodes reported:

1. Starting Day 1 and ending Day 2 (2 days)
2. Starting Day 5 and ending Day 9 (5 days)

Only the length of the longest duration (the second episode) is considered, while the first episode is not. Each duration of episode is calculated via the formula:

$$\text{Duration}(days) = (\text{end date of Solicited AE recorded in Memory Aid}) - (\text{start date of Solicited AE recorded in Memory Aid}) + 1$$

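### The reactogenicity assessment made before each dose is not used in the solicited-AE rules, so an unchanged symptom that began between doses counts as a booster reaction

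*SAP*

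**What the plan says.** Protocol 10.1: "Pre-administration reactogenicity assessments will be performed prior to each study vaccination to establish baseline".

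The solicited-AE rules do not mention that assessment again:

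- **Incidence and grade (SAP 9.1.2).** The SAP gives the number and percentage of "participants who reported any solicited AE on the vaccination day and through the 7 subsequent days", with each subject counted once per symptom at the most severe grade. Protocol 12.4.2 also takes the most severe response, "dichotomizing into a binary variable (none versus mild, moderate, or severe".
- **Duration (SAP 9.1.2).** This is the longest run of consecutive days on which the "reported solicited AE occurs with a toxicity grade > 0". Each episode runs from the "start date of Solicited AE recorded in Memory Aid" to the corresponding end date.

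SAP 9.1 holds three general rules that bear on existing symptoms:

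- **Pre-existing conditions.** "Any medical condition that is present at the time that the subject is screened will be considered as baseline and not reported as an AE" (protocol 11.1.1, repeated in SAP 9.1), unless severity increases.
- **Treatment emergence.** A TEAE is "any new AE that begins after the first vaccination or any pre-existing condition that worsens in severity".
- **Table filter.** "Only TEAEs will be included in summary tables and will be summarized by cohort and vaccination".

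SAP 4.2 (Table 2) fixes baseline at the last value on or before the prime dose. It has no second baseline for the booster.

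**The concern.** Solicited local and systemic reactions are the first two primary endpoints, and the trial has no control arm. The pre-dose assessment is the only within-subject reference that could separate a reaction from a symptom already there. Laboratory values and vital signs get change-from-baseline and shift tables (SAP 9.2 and 9.3). Solicited AEs get neither, and no output listed in SAP Appendix 2 names pre-dose grades.

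Such cases are foreseeable. Protocol 7.2.2 allows dosing during a minor illness or with minor residual symptoms. The booster follows the prime by about 16 weeks in Cohorts 1 and 2 and by 28 days in Cohorts 3, 4 and 6, so an unrelated symptom has time to start. The reactogenicity results also inform the dose for later studies (protocol 6.1).

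**Working it through.** **Step 1. Follow two subjects through the text.**

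*Symptom begins after the prime, is Grade 1 before the booster, and stays Grade 1.*
- Pre-existing rule: absent at screening, so not excluded.
- TEAE definition: began after the first vaccination, so it qualifies and passes the table filter.
- SAP 4.2 baseline: set at the prime, so it does not see the symptom.
- SAP 9.1.2: reported within the booster window, so it is counted at Grade 1. Every memory-aid day adds to duration.

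*Symptom is present before the prime and unchanged afterwards.*
- If present at screening, the pre-existing rule excludes it on its face.
- If it began between screening (up to 30 days before Day 1) and the dose, that rule does not reach it, but it is not new after the first vaccination. The TEAE filter therefore excludes it on its face.
- Three things blur this. The list of AE types in SAP 9.1 attaches treatment emergence to unsolicited events only. SAP 9.1.2 dates episodes from a memory aid handed out on the dosing day. SAP 4.1.3 makes an AE with a missing start time on the vaccination day a TEAE unless it ended before the vaccination time. Two programmers could tabulate this subject differently.

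**Step 2. Reproduce the plan's own figures.**
- Probability of at least one event in 10 at a 20% rate: 1 − 0.80^10 = 0.8926, the 89% stated in SAP 4.3.
- Duration example in SAP 9.1.2: Day 9 − Day 5 + 1 = 5 days, as stated.

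Neither figure depends on this point.

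**Step 3. Effect on duration.** The example's daily grades are 1, 1, 0, 0, 1, 2, 2, 1, 1, 0. Suppose the subject had Grade 1 headache before that dose (an assumption; the example is silent). The days above Grade 1 are Days 6 and 7, so the duration above the pre-dose grade is 7 − 6 + 1 = 2 days instead of 5.

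**Step 4. Effect of one subject in a cohort of 10** (Clopper-Pearson, the SAP's method).
- 0/10, 95% CI 0 to 30.8%, becomes 1/10, 0.3 to 44.5%.
- 3/10, 6.7 to 65.2%, becomes 4/10, 12.2 to 73.8%.

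**Step 5. Range under an assumed prevalence.** Let b be the share of subjects with a given symptom before the dose that persists unchanged. The documents give no value, so b is an assumption. Let t be the true reaction rate, independent of b. The chance of at least one such subject in 10 is 1 − (1 − b)^10. The rise in the observed rate is b(1 − t), shown for an assumed t of 30%.

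| b | At least 1 in 10 | Rise in rate, t = 30% |
|---|---|---|
| 2% | 18.3% | 1.4 points |
| 5% | 40.1% | 3.5 points |
| 10% | 65.1% | 7 points |
| 20% | 89.3% | 14 points |
| 30% | 97.2% | 21 points |

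For the case that the text clearly lets through, b covers only symptoms that began between doses and were unchanged at the booster.

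**The case against.** The best defence is that SAP 9.1 already contains the rule that seems to be missing. It lists solicited AEs among adverse events, treats conditions present at screening as baseline unless they worsen, and admits only TEAEs to summary tables. A reader might infer that long-standing, unchanged Grade 1 arthralgia in an older subject is counted after both doses. On the face of those rules it is neither new nor worse at either dose, so the documents do not support that reading. Nor does the phrase about grades above 0 govern incidence: it belongs to the duration calculation. The any-grade incidence reading rests on the wording of SAP 9.1.2 together with protocol 12.4.2.

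Counting every reported symptom is also defensible in a Phase 1 safety study. An above-baseline count can hide a real reaction. A subject with a passing Grade 1 headache at dosing, followed by several days of vaccine-induced Grade 1 headache, would drop out. This stands, and it argues against replacing the primary count.

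The scope has limits too. Injection-site items are unlikely to have a standing background. No comparison of age groups is among the stated objectives, and protocol 12.1 rules out hypothesis tests between cohorts. The numerical Grade 3 halting criteria (protocol 11.6.1) use unsolicited AEs and laboratory abnormalities.

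The defence does not reach the symptom that began between doses, and it does not reconcile 9.1 with 9.1.2.

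**Conclusion.** The point holds in a limited form. No incidence, grade or duration rule uses the pre-dose assessment. At the booster, an unchanged symptom that began after the prime is tabulated as a reaction with full duration. At the prime the text is ambiguous, which is not the same as an established upward bias. The systemic endpoint carries most of the effect; the local endpoint is little affected.

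The size cannot be stated from the documents. The firm figure is the effect of one subject in a cohort of 10, and the prevalence table only illustrates a range.

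A reader might go further and compute the share of subjects with any systemic symptom and no vaccine effect. Eight independent items at an assumed 5% to 10% background each give 1 − 0.95^8 = 34% to 1 − 0.90^8 = 57%. The documents do not support that figure. The prevalences are assumed, and the symptoms plausibly occur together; with full overlap the share is only 5% to 10%. Fever is one of the eight, yet protocol 7.2.2 says subjects should be afebrile for 72 hours before dosing. Without fever, the independent figures fall to 1 − 0.95^7 = 30% and 1 − 0.90^7 = 52%.

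**What to change.** In SAP 9.1.2:

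1. Keep the any-grade count as primary, consistent with protocol 12.4.2, and label it as including symptoms present before the dose.
2. Add to Tables 14.3.1.1 to 14.3.1.4, for each dose, the number of subjects with a pre-dose grade above 0 for each symptom.
3. Add a supportive row counting only events that are new or above the grade assessed before that same dose, with duration as consecutive days above that grade.
4. Report missing pre-dose assessments as missing. Setting them to 0 would conflict with the no-imputation rule in SAP 4.1.3.
5. State how the pre-existing-condition and TEAE rules of SAP 9.1 apply to memory-aid data at the prime and at the booster.

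The cost is SAP wording, a derived variable and a few table rows. Protocol 10.1 already requires the assessments, but it does not say that each item is graded on the memory-aid scale or entered in the eCRF. That should be confirmed before items 2 and 3 are programmed. The supportive row can miss a true reaction that only matches a passing pre-dose symptom, which is why the any-grade count stays primary.
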